9.7. Analysis of Efficacy Endpoints

Tetanus antibody titers (IU/mL) will be presented as geometric mean (GeoMean), minimum and maximum concentrations after each vaccination at all collection time points. Linear plots of the geometric mean \pm Standard errors of Tetanus antibody titers will be provided by each collection time points.

The numbers and percentages of subjects whose post vaccination anti-tetanus antibody levels are <5 IU/mL; \geq 5 IU/mL to 10 IU/mL; >10 IU/mL to 15 IU/mL; and, >15 IU/mL will be presented in a table over time. The percentages of subjects in each of these categories will also be presented in scatter plot over collection time.

10. Handling of Missing Data and Missing Date

Missing Data will not be imputed.

Missing dates are handled as follows:

- Missing day: The first day of the month will be used.
- Missing Month: The first month of the year will be used.
- Completely missing dates will remain missing, with no imputation applied. Consequently, time to onset and duration of such events will be missing.

11. Validation of Programming Code

All SAS code used to generate tables, listings, and figures will be validated and reviewed before being finalized. The validation process will be used to determine that the numbers are produced by a statistically valid method and that the execution of the computations is correct. Qualified personnel who have not previously been involved in the production of the original programming code will perform the validation procedures. Methods of validation include independent programming and comparison to data listings. Tables will be reviewed for accuracy, consistency with this plan, consistency within tables, and consistency with corresponding output. Once validation is complete, a quality control reviewer will perform a final review of the documents for accuracy and consistency. Upon completion of validation and quality review procedures, all documentation will be collected and filed in the study documentation files at Fast-Track.

12. Changes to Planned Analyses

There are no changes between protocol-defined statistical analyses and those presented in this SAP.

13. Appendix A: Table and Figure Shells

List of Tables and Figures

Table 1:	Summary of Subject Disposition – All Consented Subjects	17
Table 2:	Reasons for Not Meeting Eligibility Criterion – Not Enrolled Subjects	18
Table 3:	Demographics and Subject Characteristics	19
Table 4:	Summary of Protocol and Treatment Compliance	20
Table 5:	Summary of Plasmapheresis Check by Visit.....	21
Table 6:	Summary of Treatment-emergent Adverse Events – ITT Population	22
Table 7:	Summary of Solicited Treatment-emergent Adverse Events – ITT Population.....	23
Table 8:	Summary of Treatment-emergent Adverse Events by System Organ Class and Preferred Term – ITT Population.....	24
Table 9:	Summary of Solicitedd Treatment-emergent Adverse Events by System Organ Class and Preferred Term – ITT Population.....	25
Table 10:	Summary of Subjects with Treatment-emergent Adverse Events by Severity and Relationship - ITT Population	26
Table 11:	Contingency Table of Table of Reactogenicity and Anti-diphtheria titers - ITT Population	27
Table 12:	Summary of Serum Creatinine and Urinalysis Tests – ITT Population	28
Table 13:	Summary of Anti-tetanus Antibody Titers (IU/mL).....	29
Table 14:	Summary of Anti-diphtheria Antibody Titers (IU/mL).....	30
Table 15:	Number (%) of Subjects with Post Vaccination Anti-tetanus Antibody Levels	31
Figure 1:	Regression Plot of Reactogenicity versus Anti-diphtheria titers - ITT Population	32
Figure 2:	Plot of GeoMean (\pm SD) of Tetanus Antibody Titers	33
Figure 3:	Scatter Plot of Percentage of Subjects with Post Vaccination Anti-tetanus Antibody Levels – ITT Population	34
Figure 4:	Scatter Plot of Percentage of Subjects with Post Vaccination Anti-tetanus Antibody Levels – Per-protocol Population.....	35

Table 1: Summary of Subject Disposition - All Consented Subjects

Disposition Category	Total
Total Consented	xx
Total Eligible	xx
Enrolled and Received First Vaccination	xx
Data below is n (%) of enrolled	
Intention-to-treat (ITT) Population	xx (x.x)
Per-protocol (PP) Population	xx (x.x)
Subjects completing study (Completed Month 18 visit)	xx (x.x)
Subjects terminating early ^a	
AE or SAE	xx (x.x)
Protocol violation	xx (x.x)
Subject did not comply with protocol	xx (x.x)
Continued participation will pose a risk to the subject	xx (x.x)
Pregnancy	xx (x.x)
Subject withdrew participation	xx (x.x)
Subject no longer eligible for study participation	xx (x.x)
Other	xx (x.x)

^aSubjects may have been terminated for more than one reason, thus numbers will not add up to the total numbers of subjects.

<Program Name: Time and Date>

Table 2: Reasons for Not Meeting Eligibility Criterion - Not Enrolled Subjects

Reason	n= xx
Informed consent Withdrawn	xx (x.x%)
(List all reasons)	xx (x.x%)

<Program Name: Time and Date>

Table 3: Demographics and Subject Characteristics

Characteristic	ITT N=xx	Per-protocol N=xx
Gender		
Male	xx (x.x%)	xx (x.x%)
Female	xx (x.x%)	xx (x.x%)
Age (years at date of consent)		
Mean (SD)	xx.x (x.xx)	xx.x (x.xx)
Median	xx.x	xx.x
Min-Max	(xx – xx)	(xx – xx)
Maximum		
Race		
Black or African American	xx (x.x%)	xx (x.x%)
American Indian or Alaskan Native	xx (x.x%)	xx (x.x%)
Asian	xx (x.x%)	xx (x.x%)
Native Hawaiian or Other Pacific Islander	xx (x.x%)	xx (x.x%)
White	xx (x.x%)	xx (x.x%)
Other/Unknown	xx (x.x%)	xx (x.x%)
	xx (x.x%)	xx (x.x%)
Ethnicity		
Hispanic or Latino	xx (x.x%)	xx (x.x%)
Not Hispanic or Latino	xx (x.x%)	xx (x.x%)
Not Reported	xx (x.x%)	xx (x.x%)

<Program Name: Time and Date>

Table 4: Summary of Protocol and Treatment Compliance

	ITT N=xx
Protocol compliance rate^a	
Month 0	xx.x%
Month 3	xx.x%
Month 6	xx.x%
Month 9	xx.x%
Month 12	xx.x%
Number of Tdap vaccinations	
Mean (SD)	xx.x (x.xx)
Median	xx.x
Min-Max	(xx – xx)
Total Tdap vaccination dose (mL)	
Mean (SD)	xx.x (x.xx)
Median	xx.x
Min-Max	(xx – xx)

^aProtocol compliance is presented as percentages of subjects attending each scheduled treatment visit.

<Program Name: Time and Date>

Table 5: Summary of Plasmapheresis Check by Visit - ITT Population

Visit		n (%)
Screening	Eligible for Plasmapheresis	
	Yes	xx.x (x.xx)
	No, Temporary	xx.x (x.xx)
	No, Permanent	xx.x (x.xx)
	If "No, Temporary", Inclusion Criteria not Met	
	Temperature: 97.0 - 99.5 °F	xx.x (x.xx)
	Blood Pressure: 90 - 180/50 - 90 mmHg	xx.x (x.xx)
	Pulse: 50 - 100 beats/min	xx.x (x.xx)
	(List all criteria not met)	
(Repeat for all visits)		

<Program Name: Time and Date>

Table 6: Summary of Treatment-emergent Adverse Events - ITT Population

	Vaccination Number					Overall N=xx
	1 N=xx	2 N=xx	3 N=xx	4 N=xx	5 N=xx	
Number of AEs	xx	xx	xx	xx	xx	xx
Number of SAEs	xx	xx	xx	xx	xx	xx
Number of AEs related to study product	xx	xx	xx	xx	xx	xx
Number (%) of subjects with						
At least one AE	xx (x.x%)	xx (x.x%)	xx (x.x%)	xx (x.x%)	xx (x.x%)	xx (x.x%)
At least one SAE	xx (x.x%)	xx (x.x%)	xx (x.x%)	xx (x.x%)	xx (x.x%)	xx (x.x%)
At least one AE related to study product	xx (x.x%)	xx (x.x%)	xx (x.x%)	xx (x.x%)	xx (x.x%)	xx (x.x%)
Number of AEs by severity						
Mild	xx	xx	xx	xx	xx	xx
Moderate	xx	xx	xx	xx	xx	xx
Severe	xx	xx	xx	xx	xx	xx
Number of AEs by relationship to study product						
Unrelated	xx	xx	xx	xx	xx	xx
Unlikely	xx	xx	xx	xx	xx	xx
Possible	xx	xx	xx	xx	xx	xx
Probable	xx	xx	xx	xx	xx	xx
Definite						
Serious?						
Yes	xx	xx	xx	xx	xx	xx
No						

Note: AEs occurring after each vaccination up to the time of the next vaccination is summarized.

<Program Name: Time and Date>

Table 7: Summary of Solicited Treatment-emergent Adverse Events - ITT Population

	Vaccination Number					Overall N=xx
	1 N=xx	2 N=xx	3 N=xx	4 N=xx	5 N=xx	
Number of Solicited TEAEs	xx	xx	xx	xx	xx	xx
Number of AEs related to study product	xx	xx	xx	xx	xx	xx
Number (%) of subjects with						
At least one solicited TEAE	xx (x.x%)	xx (x.x%)	xx (x.x%)	xx (x.x%)	xx (x.x%)	xx (x.x%)
At least one AE related to study product	xx (x.x%)	xx (x.x%)	xx (x.x%)	xx (x.x%)	xx (x.x%)	xx (x.x%)
Number of Solicited TEAEs by severity						
Mild	xx	xx	xx	xx	xx	xx
Moderate	xx	xx	xx	xx	xx	xx
Severe	xx	xx	xx	xx	xx	xx
Number of Solicited TEAEs by						
relationship to study product	xx	xx	xx	xx	xx	xx
Unrelated	xx	xx	xx	xx	xx	xx
Unlikely	xx	xx	xx	xx	xx	xx
Possible	xx	xx	xx	xx	xx	xx
Probable	xx	xx	xx	xx	xx	xx
Definite						

N = Number of Subjects

Note: Solicited AEs reported within the 3 day period after each vaccination is summarized.

<Program Name: Time and Date>

Table 8: Number (%) of Subjects with Treatment-emergent Adverse Events by System Organ Class and Preferred Term - ITT Population

System, Organ, Class/ Preferred Term	Vaccination Number					Overall N=xx n (%)
	1 N=xx n (%)	2 N=xx n (%)	3 N=xx n (%)	4 N=xx n (%)	5 N=xx n (%)	
SOC 1	xx (xx.x)					
Preferred Term 1	xx (xx.x)					
SOC 2	xx (xx.x)					
Preferred Term 2	xx (xx.x)					

Note: Subjects are counted only once within each system organ class and preferred term.

<Program Name: Time and Date>

Table 9: Number (%) of Subjects withSolicited Treatment-emergent Adverse Events by System Organ Class and Preferred Term - ITT Population

System, Organ, Class/ Preferred Term	Vaccination Number					Overall N=xx n (%)
	1 N=xx n (%)	2 N=xx n (%)	3 N=xx n (%)	4 N=xx n (%)	5 N=xx n (%)	
SOC 1	xx (xx.x)					
Preferred Term 1	xx (xx.x)					
SOC 2	xx (xx.x)					
Preferred Term 2	xx (xx.x)					

: Note: Solicited AEs reported within the 3 day period after each vaccination is summarized.

Subjects are counted only once within each system organ class and preferred term.

<Program Name: Time and Date>

Table 10: Summary of Subjects with Treatment-emergent Adverse Events by Severity and Relationship - ITT Population

System, Organ, Class\ Preferred Term	Number of Subjects (%) (N=xx)								
	Mild		Moderate		Severe		All Grades		Total
	R	NR	R	NR	R	NR	R	NR	R + NR
SOC									
Preferred Term	xx (xx.x)	xx (xx.x)	xx (xx.x)	xx (xx.x)	xx (xx.x)	xx (xx.x)	xx (xx.x)	xx (xx.x)	xx (xx.x)

Note: Subjects are counted only once by preferred term at the highest severity grade and closest relationship to the investigational product.

R = Related to investigational product (possible, probable, definite). NR = Not related to investigational product (unrelated, unlikely).

Table 11: Contingency Table of Reactogenicity and Anti-diphtheria titers - ITT Population

Vaccination Number	Moderate to Severe Reactogenicity	Anti-diphtheria Titers		Total n (%)
		High = Yes n (%)	High = No n (%)	
1	Present	xx (xx.x)	xx (xx.x)	xx (xx.x)
	Absent	xx (xx.x)	xx (xx.x)	xx (xx.x)
	Total	xx (xx.x)	xx (xx.x)	xx (xx.x)
2	Present	xx (xx.x)	xx (xx.x)	xx (xx.x)
	Absent	xx (xx.x)	xx (xx.x)	xx (xx.x)
	Total	xx (xx.x)	xx (xx.x)	xx (xx.x)
3	Present	xx (xx.x)	xx (xx.x)	xx (xx.x)
	Absent	xx (xx.x)	xx (xx.x)	xx (xx.x)
	Total	xx (xx.x)	xx (xx.x)	xx (xx.x)
4	Present	xx (xx.x)	xx (xx.x)	xx (xx.x)
	Absent	xx (xx.x)	xx (xx.x)	xx (xx.x)
	Total	xx (xx.x)	xx (xx.x)	xx (xx.x)
5	Present	xx (xx.x)	xx (xx.x)	xx (xx.x)
	Absent	xx (xx.x)	xx (xx.x)	xx (xx.x)
	Total	xx (xx.x)	xx (xx.x)	xx (xx.x)
Overall	Present	xx (xx.x)	xx (xx.x)	
	Absent	xx (xx.x)	xx (xx.x)	
	Total	xx (xx.x)	xx (xx.x)	

Note: Reactogenicity is defined as the total count of a set of solicited AEs that are expected for up to 3 days after each vaccination. Cut points of 75th percentile of the anti-diphtheria titers is used to define high level.
 <Program Name: Time and Date>

Table 12: Summary of Serum Creatinine and Urinalysis Tests - ITT Population

Parameter (Unit)		Month 0	Month 3	Month 6	Month 9	Month 12
		n (%)				
Serum Creatinine	Low	xx (x.x)				
	High	xx (x.x)				
Specific Gravity	1.000	xx (x.x)				
	1.005	xx (x.x)				
	xx (x.x)				
pH	5	xx (x.x)				
	6	xx (x.x)				
	xx (x.x)				
Leucocytes	Negative	xx (x.x)				
	Trace	xx (x.x)				
	xx (x.x)				
Nitrite	Negative	xx (x.x)				
	Positive	xx (x.x)				
Protein (mg/dL)	Negative	xx (x.x)				
	Trace	xx (x.x)				
	xx (x.x)				
Glucose (mg/dL)	Normal	xx (x.x)				
	50	xx (x.x)				
	xx (x.x)				
Ketones	Negative	xx (x.x)				
	+/small	xx (x.x)				
	xx (x.x)				
Urobilinogen	Normal	xx (x.x)				
	1	xx (x.x)				
	xx (x.x)				
Bilirubin	Negative	xx (x.x)				
	+	xx (x.x)				
	xx (x.x)				
Blood/Hemoglobin (ery/uL)	Negative	xx (x.x)				
	Trace(blood)	xx (x.x)				
	xx (x.x)				

Table 13: Summary of Anti-tetanus Antibody Titers (IU/mL)

Visit	Statistics	ITT (N=xx)	Per-protocol (N=xx)
Screening	n	xx	xx
	Geometric Mean (SD)	xx.x (x.xx)	xx.x (x.xx)
	Min-Max	(xx.x-xx.x)	(xx.x-xx.x)
	n		
	Geometric Mean (SD)	xx	
Month 1	Minimum	xx.x (x.xx)	xx
	Maximum	xx.x	xx.x (x.xx)
		xx.x	xx.x
			xx.x
(Repeat for all visits)			

<Program Name: Time and Date>

Table 14: Summary of Anti-diphtheria Antibody Titers (IU/mL)

Visit	Statistics	ITT (N=xx)	Per-protocol (N=xx)
Screening	n	xx	xx
	Geometric Mean (SD)	xx.x (x.xx)	xx.x (x.xx)
	Min-Max	(xx.x-xx.x)	(xx.x-xx.x)
Month 1	n	xx	xx
	Geometric Mean (SD)	xx.x (x.xx)	xx.x (x.xx)
	Min-Max	(xx.x-xx.x)	(xx.x-xx.x)
(Repeat for all visits)			

[figure not shown]
<Program Name: Time and Date>

Table 15: Number (%) of Subjects with Post Vaccination Anti-tetanus Antibody Levels

Visit	Anti-tetanus Antibody Levels	ITT (N=xx)	Per-protocol (N=xx)
Screening	< 5 IU/mL	xx.x (x.xx)	xx.x (x.xx)
	≥ 5 to 10 IU/mL	xx.x (x.xx)	xx.x (x.xx)
	≥ 10 to 15 IU/mL	xx.x (x.xx)	xx.x (x.xx)
	≥ 15 IU/mL	xx.x (x.xx)	xx.x (x.xx)
Month 1	< 5 IU/mL	xx.x (x.xx)	xx.x (x.xx)
	≥ 5 to 10 IU/mL	xx.x (x.xx)	xx.x (x.xx)
	≥ 10 to 15 IU/mL	xx.x (x.xx)	xx.x (x.xx)
	≥ 15 IU/mL	xx.x (x.xx)	xx.x (x.xx)
(Repeat for all visits)			

<Program Name: Time and Date >

[figure not shown]
Figure 1: Regression Plot of Reactogenicity versus Anti-diphtheria titers - ITT Population

Note: Reactogenicity is defined as the total count of a set of solicited AEs that are expected for up to 3 days after each vaccination.

[figure not shown]
<Program Name: Time and Date>

Figure 2: Plot of GeoMean (\pm SD) of Tetanus Antibody Titers

[figure not shown]
<Program Name: Time and Date>

Figure 3: Scatter Plot of Percentage of Subjects with Post Vaccination Anti-tetanus Antibody Levels – ITT Population

<Program Name: Time and Date>

Figure 4: Scatter Plot of Percentage of Subjects with Post Vaccination Anti-tetanus Antibody Levels – Per-protocol Population

<Program Name: Time and Date>

14. Appendix B: Listing Shells

Listing 1. Subject Disposition – Enrolled Subjects.....	37
Listing 2. Reasons for Not Meeting Eligibility Criteria – All Subjects	37
Listing 3. Protocol Deviations – All Subjects.....	38
Listing 4. Demographics and Subject Characteristics– ITT Population	38
Listing 5. Baseline Medical History – ITT Population.....	39
Listing 6. Plasmapheresis Check – ITT Population.....	39
Listing 7. Previous Immunizations – ITT Population.....	40
Listing 8. Tdap Vaccination – ITT Population	40
Listing 9. Serum Creatinine and Urinalysis Tests Results – ITT Population	41
Listing 10. Anti-tetanus and Anti-diphtheria Antibody Tests Results – ITT Population	41
Listing 11. Adverse Events – ITT Population.....	42
Listing 12. Solicited Adverse Events – ITT Population	42
Listing 13. Adverse Events Leading to Withdrawal – ITT Population.....	43
Listing 14. Serious Adverse Events – ITT Population.....	44
Listing 15. Concomitant Medications – ITT Population	45

Listing 1: Subject Disposition –Enrolled Subjects

Subject Number	Consent to Study Date	ITT Subject	Per-protocol Subject	Date of Last Visit/Contact	Study Completed?	Reasons for Early Discontinuation	Reason Detail
xxxx	ddmmmyyyy	Y/N	Y/N	ddmmmyyyy	Y/N	xxxxxxxx	xxxx

Programming Note: Subject ID.

<Program Name: Time and Date>

Listing 2: Reasons for Not Meeting Eligibility Criteria – All Subjects

Subject Number	Reason for Screen Failure	Other Description
xxxx	Subject withdrew consent (list all reasons)	Other: Verbatim text

Programming Note:sorted by Subject number.

<Program Name: Time and Date>

Listing 3: Protocol Deviations – All Subjects

Subject Number	Deviation Date	Deviation Detail
xxxx	dd/mmm/yyyy	Verbatim text

Note: Only subjects with protocol deviations are listed.

Programming Note: Sorted by Subject number.

<Program Name: Time and Date>

Listing 4: Demographics and Subject Characteristics- ITT Population

Subject Number.	Age at Date of Consent (Years)	Gender	Race	Ethnicity
xxxx	xx	Male	White	Hispanic or Latino
		Female	Other	Not Hispanic or Latino
				Not Recorded

Programming Note: Sorted by subject number. Insert verbatim when “Other” race is selected.

<Program Name: Time and Date>

Listing 5: Baseline Medical History – ITT Population

Subject Number	History Verbatim Term	Start Date	Stop Date	Start Day (relative to start of treatment)	Stop Day (relative to start of treatment)	Ongoing?
xxxx	xxxx	dd/mmm/yyyy	dd/mmm/yyyy	xxx	xxx	Y/N

<Program Name: Time and Date>

Listing 6: Plasmapheresis Check – ITT Population

Subject Number	Visit	Date of Plasmapheresis Check	Eligible for Plasmapheresis	Inclusion Criteria Not Met
xxxx		dd/mmm/yyyy	Yes	XXXXXXX

<Program Name: Time and Date>

Listing 7: Previous Immunizations – ITT Population

Subject Number	Date of Previous Immunization	Type of Previous Immunization
xxxx	dd/mmm/yyyy	

Programming Note: Sorted by subject number, exam date.

<Program Name: Time and Date>

Listing 8: Tdap Vaccination – ITT Population

Subject Number	Date of Tdap Vaccination	Visit	Tdap NDC Number	Tdap Lot Number	Problems with the injection?	Specify
xxxx	dd/mmm/yyyy	Month 0			Y/N	Verbatim text

Programming Note: Sorted by subject number, exam date.

<Program Name: Time and Date>

Listing 9: Serum Creatinine and Urinalysis Tests Results – ITT Population

Subject Number	Date of Collection	Visit	Test Name (Unit)	Result	Reason not Collected
xxxx	dd/mmm/yyyy	Screening (all Visits)	Creatinine (Unit) Glucose	Xxx Xxx	Xxx Xxx/xx

Programming Note: Sorted by subject number, Exam Date .

<Program Name: Time and Date>

Listing 10: Anti-tetanus and Anti-diphtheria Antibody Tests Results – ITT Population

Subject Number	Date of Collection	Visit	Plasma Sample Identification #	Test Name (Unit)	Result	Reason not Collected, Specify
xxxx	dd/mmm/yyyy	Screening (all Visits) Unscheduled		xxx xxx/xx	Xxx Xxx/xx	Xxx Xxx/xx

Programming Note: Sorted by subject number, Exam Date.

<Program Name: Time and Date>

Listing 11: Adverse Events – ITT Population

Subject Number	AE Name/ MedDRA PT ^a / SOC ^b	Onset Date/ Stop Date	Onset Day/ Duration (Days)	Severity	TEAE/ Vaccine Number	Serious? /SAE Description	Outcome	Relationship to Study Product/ Action Taken	Other Actions, Specify
xxxx	xxxx/	dd/mmm/yyyy	Xx/xx	Mild		Y/Xxx	Resolved	Unrelated	
	xxxx /	dd/mmm/yyyy		Moderate		N	Resolved	Unlikely	
	xxxx	or Ongoing		Severe			with sequelae	Possible Probable	

^aPT=Preferred Term; ^bSOC=System, Organ, and Class

Programming Note: Sorted by Subject Number, Onset Date.

<Program Name: Time and Date>

Listing 12: Solicited Adverse Events – ITT Population

Subject Number	Vaccination Number	AE Name/ MedDRA PT ^a / SOC ^b	Onset Date/ Stop Date	Onset Day/ Duration (Days)	Severity	TEAE/ Vaccine Number	Serious?	Outcome	Relationship to Study Product/ Action Taken
xxxx	1	xxxx/	dd/mmm/yyyy	Xx/xx	Mild		Y	Resolved	Unrelated
	2	xxxx /	dd/mmm/yyyy		Moderate		N	Resolved with sequelae	Unlikely Possible Probable
		xxxx	or Ongoing		Severe				

^aPT=Preferred Term; ^bSOC=System, Organ, and Class

Note: Solicited AEs reported within the 3 day period after each vaccination is listed.

Programming Note: Sorted by Subject Number, Onset Date.

<Program Name: Time and Date>

Listing 13: Adverse Events Leading to Withdrawal – ITT Population

Subject Number	AE Name/ MedDRA PT ^a / SOC ^b	Onset Date/ Stop Date	Onset Day/ Duration (Days)	Severity	TEAE/ Vaccine Number	Serious?	Outcome	Relationship to Study Product/ Action Taken	Other Actions, Specify
xxxx	xxxx/	dd/mmm/yyyy	Xx/xx	Mild		Y/Xxx	Resolved	Unrelated	
	xxxx /	dd/mmm/yyyy		Moderate		N	Resolved	Unlikely	
	xxxx	or Ongoing		Severe			with sequelae	Possible Probable	

^aPT=Preferred Term

^bSOC=System, Organ, and Class

Programming Note: Sorted by Subject Number, Onset Date.

<Program Name: Time and Date>

Listing 14: Serious Adverse Events – ITT Population

Subject Number	Age (Years) at Screening	Gender	SAE Name	SAE Description	Considered serious because	Onset Date/Stop Date	Vaccination Number	Death Date
xxxx	xx	Male	Verbatim text	Verbatim text	Death	dd/mmm/yyyy/ dd/mmm/yyyy		dd/mmm/yyyy
		Female			Life-threatening Hospitalization-initial or prolonged Disability or permanent damage Congenital anomalies or birth defects Other medically important condition			

Programming Note: Sorted by Group, Subject ID.
<Program Name: Time and Date>

Listing 14: Serious Adverse Events – ITT Population (continued)

Subject Number	SAE Name	Hospitalized Date	Discharge Date	Continued Study Participation	Outcome	Relationship to Study Drug	Important Medical Event?
xx	Verbatim text	dd/mmm/yyyy	dd/mmm/yyyy	Y/N	Resolved Resolved with sequelae	Unrelated Unlikely Possibly Related Probably Related Definitely Related	

Programming Note: Sorted by Subject Number.
<Program Name: Time and Date>

Listing 15: Concomitant Medications – ITT Population

Subject Number	Prior Med?	Verbatim Medication Name	Indication	Route	Dose	Frequency	Start Date	Stop Date
xxx	Y N	xxx	xxxxxx	xxxxxx	xxxxxx	xxxxxx	dd/mmm/yyyy	dd/mmm/yyyy or Ongoing

Programming Note: Sorted by Subject Number, Start Date.

<Program Name: Time and Date>

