Investigational product, dosage and mode of administration: Tdap is Diphtheria and Tetanus Toxoids and Acellular Pertussis vaccine approved by FDA that is manufactured by Sanofi Pasteur Limited. It is administered as a 0.5 mL dose intramuscularly.
Duration of treatment: The vaccine will be administered every three months \pm 1 week for 12 months (5 vaccinations).
Criteria for evaluation: Safety: Safety endpoints include: 
Incidence, severity, and relationship of AEs to the study vaccine in the time period between vaccinations and for the overall study period. Efficacy endpoints include: 
Anti-tetanus antibody titer levels after each vaccination presented at geometric means (GeoMean) over time.The numbers and percentages of subjects whose post vaccination antibody levels are <5 IU/mL; \geq5 IU/mL to 10 IU/mL; >10 IU/mL to 15 IU/mL; and, >15 IU/mL after each vaccination.

Statistical methods:

In general all data will be summarized by mean, standard deviation (SD), median, minimum and maximum values for continuous variables and by numbers and percentages for categorical data and will be presented in listings for all subjects.

Analysis Populations:

The intention-to-treat (ITT) population will consist of all subjects who are enrolled into the study and received any amount of investigational product.

The per-protocol (PP) population will consist of all subjects in the ITT population who received all five (5) Tdap vaccinations and completed the 6 month follow-up visit after the final vaccination.

Baseline Data:

Demographic, other baseline data and record of vaccinations for all subjects will be summarized in tables.

Safety Data:

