12.2.4. Analysis of Efficacy Endpoints

Tetanus antibody titers (IU/mL) will be presented as geometric mean (GeoMean), minimum and maximum concentrations after each vaccination at all collection time points and graphically as GeoMean \pm standard errors.

The numbers and percentages of subjects whose post vaccination anti-tetanus antibody levels are <5 IU/mL; \geq 5 IU/mL to 10 IU/mL; >10 IU/mL to 15 IU/mL; and, >15 IU/mL will be presented in a table over time. The percentages of subjects in each of these categories will also be presented graphically over time.

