9.1. General Considerations

Descriptive statistics will be used to present study data. Continuous variables will be presented as number of observations (n), mean, standard deviation (SD), median, minimum (min) and maximum (max) values. Categorical and dichotomous variables will be presented as counts and percentages. As it is expected that titers will not be normally distributed, geometric means (GeoMean) will be used to summarize anti-tetanus and anti-diphtheria antibody titers. All data will be presented in listings.

Analyses will be done using SAS v9.4.

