9.5. Analysis of Safety Endpoints

Treatment emergence will be evaluated for all AEs. Treatment-emergent adverse events (TEAEs) are those that occur on or after the same date and time of first dose of study drug. TEAEs will be coded using the most recent version of the Medical Dictionary of Regulatory Affairs (MedDRA) by assigning a preferred term and will be grouped by system, organ, and class (SOC) designation. AEs occurring after each vaccination up to the time of the next vaccination and separately over the whole study period will be summarized. Separate tables will be provided for solicited AEs reported within the 3 day period after each vaccination.

Each AE will be counted once only by preferred term for a given study subject within each post vaccination time period prior to the next vaccination or up to the 6-month follow-up visit after the last vaccination. If the same AE occurred on multiple occasions, the highest severity and relationship to investigational product will be assumed within each time period.

The summary tables will include an overall summary of number and percentage of subjects reporting each TEAE, summary by relationship, summary by severity will be presented by each vaccination period and overall.

Listings of each individual AE including start date, stop date, severity, relationship, duration, outcome, and actions taken will be provided.

Reactogenicity is defined as the total count of a set of solicited AEs that are expected after a vaccine. A regression analysis will be performed with reactogenicity as the dependent variable and anti-diphtheria titers as the independent variable to determine if there is an association. Anti-diphtheria titer is not expected to be normally distributed and will be natural log transformed. Null Hypothesis of no association between reactogenicity and anti-diphtheria titers will be tested on

Slope obtained using simple linear regression analysis at alpha=0.01 using two-sided tests. The null hypothesis states that the slope is equal to zero, and the alternative hypothesis states that the slope is not equal to zero. No adjustment for covariates will be made. The following SAS procedure PROC REG may be used.

```
Proc reg data=data;
Model reactogenicity =log(anti_diphtheria_titers);
Run;
```

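### SAP output shells disagree with the planned anti-tetanus analysis: Figure 2 shows SD instead of standard errors, and Table 15 uses different titre bands

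*SAP*

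**What the plan says.** **Error bars.** SAP 9.7 plans a plot of the geometric mean anti-tetanus titre, and "Standard errors of Tetanus antibody titers will be provided by each collection time points". Protocol 12.2.4 says the same, "graphically as GeoMean \pm standard errors", as does the Efficacy Data paragraph of the protocol synopsis. In SAP Appendix A, Figure 2 is titled "Plot of GeoMean (\pm SD) of Tetanus Antibody Titers", both in the list of tables and figures and on the shell itself.

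**Tables 13 and 14.** These shells have a row that begins "Geometric Mean (SD". Neither the shells nor the SAP text says what kind of SD this is. SAP 9.1 mentions an SD only in its general list: "Continuous variables will be presented as number of observations (n), mean, standard deviation (SD), median, minimum (min) and maximum (max) values". It then calls for geometric means for titres without naming a companion measure of spread.

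**Titre bands.** The endpoint has four bands: <5, ≥5 to 10, >10 to 15 and >15 IU/mL. The upper two appear in the synopsis criteria for evaluation as ">10 IU/mL to 15 IU/mL; and, >15 IU/mL after each vaccination". The same bands are in Protocol 9.1 and 12.2.4 and in SAP 3.3 and 9.7. The Table 15 shell has <5, ≥5 to 10, ≥10 to 15 and ≥15, repeated in both visit blocks. The Efficacy Data paragraph of the synopsis also has ≥10 to 15 and ≥15, with ≤5 as its lowest band.

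**Changes.** SAP section 12 declares no departures from the protocol's analyses.

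**The concern.** Programmers build outputs from the shells. If Figure 2 is built as titled, the bars will show how widely individual donors' titres vary, whereas the plan promises the precision of the geometric mean at each visit. A reader who takes them for standard errors would think the titre curve far less precisely estimated than it is.

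The scale is also open. The SAP does not say whether the SE, or the SD beside the geometric mean in Tables 13–14, is computed on log titres and back-transformed or on raw IU/mL. A raw-scale SD is the wrong companion to a geometric mean and could put the lower bar below zero.

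For Table 15, a titre of exactly 10 or 15 is counted twice if the upper limits are inclusive, or moves up one band if they are exclusive. Either way the table does not report the defined endpoint, and in the first case the percentages can sum to more than 100%.

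These outputs carry the trial's only secondary objective.

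**Working it through.** The documents give no figure to reproduce here, so the check compares the passages and then sizes the difference.

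**1. Error bars, side by side**

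| Place | Bars |
|---|---|
| Synopsis, Efficacy Data | ± SE |
| Protocol 12.2.4 | ± SE |
| SAP 9.7 | ± SE |
| SAP Appendix A, list of figures, Figure 2 | ± SD |
| SAP Appendix A, Figure 2 shell | ± SD |

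**2. Size of the SD/SE difference.** On the ln scale SE = SD/√n, so SD/SE = √n. The planned n is 100 (SAP section 7); 80 and 60 illustrate fewer contributing subjects.

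- n = 100: √100 = 10.0
- n = 80: √80 = 8.9
- n = 60: √60 = 7.7

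**3. After back-transformation.** This step assumes lognormal titres. The documents give neither the geometric mean nor s, the SD of ln(titre), so s = 0.5 to 1.2 is an assumed range. At n = 100 the ratio of bar widths is

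(e^s − e^(−s)) / (e^(s/10) − e^(−s/10))

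| s | SD bar width / SE bar width |
|---|---|
| 0.5 | 10.42 |
| 0.8 | 11.09 |
| 1.0 | 11.73 |
| 1.2 | 12.55 |

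Example with an assumed geometric mean of 10 IU/mL and s = 0.8:

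- SE bar: 10·e^(±0.08) = 9.23 to 10.83
- SD bar: 10·e^(±0.8) = 4.49 to 22.26, which reaches into all four endpoint bands

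**4. If the SD were on the raw scale.** For a lognormal titre, raw SD = GeoMean·e^(s²/2)·√(e^(s²) − 1). It equals the geometric mean when e^(s²)·(e^(s²) − 1) = 1, so e^(s²) = (1 + √5)/2 = 1.618 and s = 0.694. Above that value, GeoMean − SD is negative.

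**5. Bands.** Titres at the cut points were assigned under each wording, with upper limits read as inclusive.

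| Titre (IU/mL) | SAP 9.7 / Protocol 9.1 | Table 15 shell | Synopsis, Efficacy Data |
|---|---|---|---|
| 5 | band 2 | band 2 | bands 1 and 2 |
| 10 | band 2 | bands 2 and 3 | bands 2 and 3 |
| 15 | band 3 | bands 3 and 4 | bands 3 and 4 |

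Only the SAP 9.7 wording puts every titre in exactly one band.

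**6. How many results the bands affect.** SAP 3.2 gives titres monthly for 11 months, then at 1 and 6 months after the last vaccination: 11 + 2 = 13 post-vaccination samples, or 100 × 13 = 1,300 results with no dropout. With an assumed geometric mean of 5–20 IU/mL and s of 0.5–1.2, and results reported to 0.1 IU/mL, the share at exactly 10 or 15 is P(9.95 to 10.05) + P(14.95 to 15.05).

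- Lowest: 0.353% (GeoMean 5, s 0.5), giving 1,300 × 0.00353 = 4.6 results
- Highest: 1.230% (GeoMean 11.65, s 0.5), giving 1,300 × 0.01230 = 16.0 results

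Reporting to 0.01 IU/mL divides these by ten: 0.46 to 1.6 results. The documents do not state the reporting precision.

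**The case against.** **Low stakes.** Anti-tetanus titre carries no hypothesis test; the only planned test is the anti-diphtheria slope. Table 13 also prints n and the range, and Listing 10 gives every titre, so a reader could rebuild the correct summary. This stands and keeps the point minor.

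**The documents already indicate which version governs.** The body text is consistent on SE, SAP section 12 declares no change from the protocol, and SAP section 11 says "Tables will be reviewed for accuracy, consistency with this plan, consistency within tables, and consistency with corresponding output", followed by a final quality review. This makes an unnoticed error less likely. But the shells are part of the plan being checked against, and no rule says that text overrides shells. For the bands, the synopsis Efficacy Data paragraph sides with Table 15 on the upper two, so the protocol is not uniform either.

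**The signs may have been misread from the PDF.** A > read as ≥ is possible in the synopsis paragraph, and so in Table 15. However, < 5 reads correctly in Table 15 and the ≥ signs recur in both visit blocks, so a true discrepancy is more likely. The band half is somewhat less certain than the SD/SE half. The Figure 2 image could not be seen, so that half rests on its title, given twice, and any footnote is unchecked.

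**The sizes are mostly assumed.** Only √n is free of assumptions about titres. The count of 1,300 ignores dropout and omits the pre-vaccination Month 12 sample described in Protocol 8.8; including it gives 1,400 results and about 5–17 boundary titres. The conclusion is unchanged.

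**Tables 13–14 do not contradict the text.** Correct. Relabelling their SD is a clarification, not the repair of a contradiction.

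**Conclusion.** The concern holds in both parts. The Figure 2 title contradicts SAP 9.7, Protocol 12.2.4 and the synopsis, and the Table 15 bands contradict the endpoint defined in SAP 3.3 and 9.7, Protocol 9.1 and 12.2.4, and the synopsis criteria for evaluation. SAP section 12 rules out reading either as a declared change.

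The error-bar mismatch matters more: 10-fold on the log scale at n = 100, and 10.4 to 12.5 times in back-transformed width for an assumed ln-SD of 0.5–1.2. The band mismatch is small, at most about 1.2% of results under the stated assumptions, and negligible if titres are reported to 0.01 IU/mL.

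This is a consistency correction to a descriptive secondary endpoint that should be made before the outputs are programmed. It leaves the primary safety results, alpha and sample size untouched.

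**What to change.** In the SAP, before database lock:

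- Change the Figure 2 title and shell to geometric mean ± SE.
- State in 9.7 that the mean and SE are computed on ln(titre) at each visit and back-transformed. SAP 9.5 already takes this approach for diphtheria: "Anti-diphtheria titer is not expected to be normally distributed and will be natural log transformed".
- In Tables 13–14, replace the SD with a geometric SD labelled as a ratio, or drop it.
- Copy the 9.7 bands (<5, ≥5 to 10, >10 to 15, >15 IU/mL) into Table 15 and use them for Figures 3–4.

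Align the synopsis Efficacy Data wording at the next protocol amendment. A back-transformed 95% confidence interval is an optional alternative; if it replaces ± SE, record the change in SAP section 12.

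The cost is a few edits to text and shells. No new data, no change in sample size and no immediate protocol amendment are needed.
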